6.1.4.1.2 Imputation for supplemental estimand

The originally pre-specified primary analysis estimand will remain unchanged, but will be re-labeled as a supplemental estimand and will handle all intercurrent events using a “Treatment Policy Strategy” (Section 8.1.1). Imputation for the supplemental estimand will be similar to the process described above for the primary estimand; however, subjects who discontinue due to lack of efficacy or adverse event will be treated the same as those who did not discontinue for one of those reasons. All observed data for these subjects will be included in the imputation process subject to the analysis visit window strategy described in Section 6.1.5.

6.1.4.2 Tipping Point Analysis

As a sensitivity analysis to the multiple imputation analysis as described in [Section 6.1.4.1](#) for the S-IGA and B-IGA co-primary endpoints, a tipping point analysis will be performed in order to determine the inflection point at which the inference under the MNAR assumption changes substantially. This will be used to check the robustness of the imputation.

The sensitivity analysis will be performed by using a specified sequence of shift parameters, which will adjust the imputed values for observations in both treatment groups. The range of shift parameters to be included in this analysis will be 0 to 2 by 0.5 for the active group and -2 to 0 by 0.5 for the vehicle group. Once the likely point of the shift is determined, the analysis may be rerun using a more focused range around the suspected tipping point. Thus, the value at which the results of the analysis are shifted from significant (i.e., $\alpha \leq 0.025$) to nonsignificant

(i.e., $\alpha > 0.025$) will be determined.

Step 1 and 3 of the analysis will be the same as for the multiple imputation analysis as described in [Section 6.1.4.1.1](#). However, [Step 2](#) of the analysis is where the shift parameters will be applied.

Pseudo-code for Step 2 is as follows:

```
proc mi data=example_1 seed=90066927 n impute=15 out=example_2;
  by <MCMC imputation>;
  class <treatment> <pooled site group.>;
  monotone regpmm(<baseline score> ..... <visit8 score>);
  var <treatment> <pooled site group> <baseline score> ..... <visit8 score>;
  mnar adjust(<visit2 score> / shift=YY adjustobs=(treatment='Roflumilast
Foam 0.3%));
  mnar adjust(<visit4 score> / shift=YY adjustobs=(treatment='Roflumilast
Foam 0.3%));
  mnar adjust(<visit8 score> / shift=YY adjustobs=(treatment='Roflumilast
Foam 0.3%));
  mnar adjust(<visit2 score> / shift=ZZ adjustobs=(treatment='Vehicle
Foam'));
  mnar adjust(<visit4 score> / shift=ZZ adjustobs=(treatment='Vehicle
Foam'));
  mnar adjust(<visit8 score> / shift=ZZ adjustobs=(treatment='Vehicle
Foam'));
run;
```

YY and ZZ will encompass all combinations of the range of shift parameters as pre-specified above.

Imputed values for subjects who discontinue due to lack of efficacy or adverse event will be handled as described in [Section 6.1.7](#) to ensure that these subjects are analyzed as non-responders at all visits on or after discontinuation of treatment.

6.1.5. Analysis Visit Windows

6.1.5.1. Non-Diary Assessments

Visits will be analyzed as scheduled (i.e., not subject to visit windowing). Unscheduled, early termination, and/or repeated measurements will only be included if a scheduled measurement is not available and the unscheduled, early termination, or repeated measurement falls within the analysis visit windows as described in [Table 2](#). Visits falling outside of these windows will not be windowed (e.g., an unscheduled visit before first application of study drug). The windows follow the Schedule of Events in [Table 1](#). Unscheduled/repeated measurements will be listed.

Table 2: Analysis Visit Windows (Study Visit) for Non-diary Assessments

| Visit Name | Visit Number | Target Start Day | Lower Limit | Upper Limit |
|------------|--------------|------------------|-------------|-------------|
| Week 2 | 3 | 15 | 2 | 22 |
| Week 4 | 4 | 29 | 23 | 42 |

| Visit Name | Visit Number | Target Start Day | Lower Limit | Upper Limit |
|------------|--------------|------------------|-------------|-------------|
| Week 8 | 5 | 57 | 43 | --- |

6.1.5.2. Diary Assessments (WI-NRS, SI-NRS)

Diary entries will be assigned to a study week for analysis based on the study day relative to the first application of study drug according to [Table 3](#).

Table 3: Analysis Window for Calculation of Average Weekly SI-NRS and WI-NRS

| Study Days for Calculation of average weekly WI-NRS | Week (Derived) |
|---|----------------|
| (-7, -1) or (-6, 1)* | Baseline |
| (2, 7) | Week 1 |
| (8, 14) | Week 2 |
| (15, 21) | Week 3 |
| (22, 28) | Week 4 |
| (29, 35) | Week 5 |
| (36, 42) | Week 6 |
| (43, 49) | Week 7 |
| (50, 56) | Week 8 |

* If the Day 1 score is collected after the first treatment application use data from days (-7, -1), otherwise use data from days (-6, 1). If Day 1 time of assessment is unknown, assume that the assessment was obtained prior to the first treatment application as prescribed by the protocol. If a subject does not have assessment performed on Day 1, then (-7, -1) window will be used in determining the average scores.

6.1.6. Pooling of Sites

Sites will be pooled for statistical analysis as follows. For analysis, sites should have a minimum of 10 randomized subjects. The smallest sites will be grouped sequentially in order of smallest to largest within each country, restricting to those sites that did not meet the minimum enrollment of 10, until each pooled site has a minimum of 10 subjects within each country with at least 1 subject in each treatment group.

6.1.7. Derived Variables

Efficacy variable derivations described in this section will be performed with one exception. The exception is that subjects who discontinued early from study due to an AE or lack of efficacy will be considered as not having response (for MI and non-responder imputation analyses) and will be excluded from observed case analyses for all pre-specified analysis visits (refer to Section

6.1.5) on or after the associated analysis visit of the subject's last dose day). More specifically, for MI and non-responder imputation analyses, these subjects will be counted as non-responders for categorical variables and set to baseline for continuous variables for all visits on or after the associated analysis visit of the subject's last dose day.

- **Study day** is calculated as:
 - observation date – first dose date + 1, if record is collected on or after first dose date
 - observation date – first dose date, if record is collected prior to first dose date.
- **S-IGA Success** = S-IGA of “Clear” or “Almost Clear” plus at least 2-grade improvement from baseline.
- **B-IGA Success** = B-IGA of “Clear” or “Almost Clear” plus at least 2-grade improvement from baseline.
- **Average Weekly SI-NRS Score** = SI-NRS scores will be assigned to a particular study week based on the study week window, as shown in [Section 6.1.5.2](#). Average weekly baseline SI-NRS is derived as the average of all non-missing scores reported during the last 7 days prior to treatment if at least 4 of 7 evaluable daily SI-NRS questionnaires are available. Daily baseline SI-NRS is defined as the last non-missing assessment prior to the first study treatment.

If 2 or more observations are present for a single day, the most severe itch score will be used as a single daily value before calculating the average weekly score. The average of the reported (non-missing) SI-NRS scores assigned to each study week will be calculated. If at least 4 SI-NRS scores are present in this time period, the average weekly SI-NRS score will be calculated; otherwise, the average weekly score will be missing for that week. The derived average score will be rounded to 1 digit. Missing average weekly scores will be imputed as described in [Section 6.1.4.1](#).

- **SI-NRS Success** = achievement of at least 4-point reduction in average weekly SI-NRS score compared to baseline, calculated only for the subjects with SI-NRS ≥ 4 at baseline.

Day 1 and 72-hour SI-NRS = the Day 1 and 72-hour endpoints are meant to measure the response to the first and first 3 treatment applications, respectively. The relevant assessments are the ones reported prior to IP application on study days 2 and 4 where study day is calculated as described earlier in this section.

- **Average Weekly WI-NRS Pruritus Score** = WI-NRS pruritus scores will be assigned to a particular study week based on the study week window, as shown in [Section 6.1.5.2](#). If 2 or more observations are present for a single day, the most severe itch score will be used for that day. The average of the reported (nonmissing) WI-NRS pruritus scores assigned to each study week will be calculated. If at least 4 WI-NRS pruritus scores are present in this time period, the average weekly WI-NRS pruritus score will be calculated similar to SI-NRS; otherwise, the average weekly score will be missing for that week. Missing average weekly scores will be imputed as described in [Section 6.1.4.1](#).

- **WI-NRS Success** = achievement of at least 4-point reduction in average weekly WI-NRS score compared to baseline, calculated only for the subjects with WI-NRS ≥ 4 at baseline.
- **PASI** = $(0.1 \times [E_h + T_h + S_h] \times A_h) + (0.2 \times [E_a + T_a + S_a] \times A_a) + (0.3 \times [E_t + T_t + S_t] \times A_t) + (0.4 \times [E_l + T_l + S_l] \times A_l)$
where E , T , and S are erythema, thickness, and scaling, respectively, scored on a scale of 0 to 4, A is estimated area of skin involved, graded on a scale of 0 to 6, and h , a , t , and l are head, arms, trunk, and legs, respectively (range for total score 0 to 72). If any of the component scores are missing, the PASI cannot be calculated.
- **PASI-50, PASI-75, PASI-90, PASI-100** = achievement of a 50%, 75%, 90%, or 100% reduction in PASI from baseline, respectively.
- **PSD Total Score** = sum of the 16 questions (individual questions scored 0 to 10, where higher scores indicate more severe symptoms; range for total score 0 to 160). If 1 or more items are missing, the score is not calculated.
- **PSD total score of 0** = achievement of a PSD total score of 0.
- **PSD scaling score of 0** = achievement of a PSD scaling score of 0.
- **PSD pain score of 0** = achievement of a PSD pain score of 0.
- **PSD itch score of 0** = achievement of a PSD itch score of 0.
- **PSD Itching/Pain/Scaling Aggregate Score** = sum of these 3 questions (individual questions that are scored 0 to 10, where higher scores indicate more severe symptoms; range for this score is 0 to 30. If 1 or more items are missing, the score is not calculated.
- **PSSI** = (erythema score + induration + desquamation) \times extent of scalp affected (range 0 to 72). Erythema, induration, and desquamation are scored on a scale of 0 to 4, where 0 = absent and 4 = severest possible; extent of scale affected is scored on a scale of 0 to 6, where 0 = 0% of involved area and 6 = 90-100% of involved area.
- **PSSI-50, PSSI-75, PSSI-90, PSSI-100** = achievement of a 50%, 75%, 90%, or 100% reduction in PSSI from baseline, respectively.
- **Scalpdex Score Transformation** = Scalpdex is rated on a 1 to 5 scale which will be transformed to 0 to 100 Scale where 1=0; 2=25; 3=50; 4=75; 5=100. This transformed score is used to calculate scale scores.
 - **Emotions Scale** = average of (Q2, Q4, Q5, Q6, Q7, Q9, Q10, Q11, Q12, Q14, Q16, Q17, Q19, Q20, Q22) after transforming to 0 to 100 scale as mentioned above. Q refers to question number. Q19 will be reverse scored i.e., 1=100; 2=75; 3=50; 4=25; 5=0.
 - **Symptoms Scale** = average of (Q1, Q3, Q8) after transforming to 0 to 100 scale as mentioned above. Q refers to question number.
 - **Functioning Scale** = average of (Q13, Q15, Q18, Q21, Q23) after transforming to 0 to 100 scale as mentioned above. Q refers to question number.
- **Scalpdex Total Score** = calculated as mean of all the 23 scalpdex questions using the transformed scale of 0 to 100. Q19 will be reverse scored i.e., 1=100; 2=75; 3=50; 4=25; 5=0 while calculating the mean. Q refers to question number.

- **DLQI Score** (Dermatology Life Quality Index for ages 17+ years) = sum of the 10 questions (individual questions scored as Very much=3, A lot=2, A little=1, Not at all=0, with Not relevant recoded to 0; Question 7: Yes=3, No=0, with Not relevant recoded to 0; range for score 0 to 30). If 1 item is missing, that item is scored as 0. If 2 or more items are missing, the score should not be calculated.
- **CDLQI Score** (Children's Dermatology Life Quality Index for ages 12-16 years) = sum of the 10 questions (individual questions scored as Very much=3, Quite a lot=2, Only a little=1, Not at all=0; Question 7: if the last week was school time, the question was scored as Very much=3, Quite a lot=2, Only a little=1, Not at all=0, with Prevented school recoded to 3, and if the last week was vacation, the standard responses apply; range for score 0 to 30). If 1 item is missing, that item is scored as 0. If 2 or more items are missing, the score should not be calculated.
- **Compliance** = number of applications divided by the expected number of IP applications for each subject. Compliance will be calculated using drug accountability data over the entire treatment period for each subject, up to treatment completion or discontinuation.
 - **Number of Expected IP Applications** = calculated as last treatment/interruption date – first treatment date + 1. If last treatment date \geq last interruption date, then the last treatment date will be used; otherwise, last interruption date will be used in deriving the expected number of IP applications.
 - **Number of IP Applications** = number of expected IP applications – missed IP applications as collected in the eCRF.
 - **Number of Days on IP** = last treatment date – first treatment date + 1.
- **Body Mass Index (BMI) (kg/m²)** = (weight in kg)/[(height in cm/100)²]. For Week 8, Week 8 height will be used to derive BMI since height is not collected at all visits.
- **BMI Categories**
 - Underweight: BMI < 18.5
 - Normal: 18.5 \leq BMI \leq 24.9
 - Overweight: 25.0 \leq BMI \leq 29.9
 - Obese: BMI \geq 30.0
- **Age Categories:**
 - 12 – 17 years
 - 18 – 64 years
 - \geq 65 years
- **Change from Baseline** = value at current time point – value at baseline.
- **Duration (months) since onset of scalp and/or body psoriasis is derived as:**
 - (Randomization date – onset date)/30.4375
 - If day of onset is not available, assume that onset occurred on the 1st of the month.
- **Treatment-emergent AE (TEAE)** = any AE with an onset date/time after the first application of IP.

- **PHQ-8** = sum of the 8 questions (individual questions scored as Not at all=0, Several days=1, More than half the days=2, and Nearly every day=3; range for score 0 to 24). If more than 1 item is missing, the score should not be calculated. If 1 item is missing, the score is calculated as (sum of answered items*8)/number of answered items.

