| Final V3.0 | 
This was a post-database lock and post-unblinding update to the SAP. The purpose is to clarify that for subjects who discontinued early from the study due to adverse event or lack of efficacy, a subject will be considered as non-responder (for MI and nonresponder imputation analyses) or missing (for observed case analyses) for all analysis visits (refer to Section 5.4) on or after the associated analysis visit of the subject's last dose day (refer to Section 6.1.5). This change to the primary estimand and multiple imputation procedure was based on recommendations from FDA during a pre-NDA meeting for a similar program held on 9/14/2022.
 |

TABLE OF CONTENTS

| | | |
|--------|--|----|
| 1. | OVERVIEW | 11 |
| 2. | STUDY OBJECTIVES AND ENDPOINTS | 12 |
| 2.1. | Study Objectives | 12 |
| 2.1.1. | Primary Objective | 12 |
| 2.2. | Study Endpoints | 12 |
| 2.2.1. | Safety Endpoints | 12 |
| 2.2.2. | Efficacy Endpoints | 12 |
| 3. | OVERALL STUDY DESIGN AND PLAN | 15 |
| 3.1. | Overall Design | 15 |
| 3.2. | Sample Size and Power | 15 |
| 3.3. | Study Population | 15 |
| 3.4. | Treatments Administered | 16 |
| 3.5. | Method of Assigning Subjects to Treatment Groups | 16 |
| 3.6. | Blinding and Unblinding | 16 |
| 3.7. | Schedule of Events | 16 |
| 4. | STATISTICAL ANALYSIS AND REPORTING | 19 |
| 4.1. | Introduction | 19 |
| 4.2. | Interim Analysis and Data Monitoring | 19 |
| 5. | ANALYSIS POPULATIONS | 19 |
| 6. | GENERAL ISSUES FOR STATISTICAL ANALYSIS | 20 |
| 6.1. | Statistical Definitions and Algorithms | 20 |
| 6.1.1. | Baseline | 20 |
| 6.1.2. | Adjustments for Covariates | 21 |
| 6.1.3. | Covariates for this study include the pooled site group (see Section 6.1.6), baseline S-IGA randomization strata (S-IGA = 3 vs. S-IGA = 4) and baseline B- IGA randomization strata (B-IGA = 2 vs. B-IGA \geq 3). Multiple Comparisons | 21 |
| 6.1.4. | Handling of Dropouts or Missing Data | 22 |
| 6.1.5. | Analysis Visit Windows | 26 |
| 6.1.6. | Pooling of Sites | 27 |
| 6.1.7. | Derived Variables | 27 |
| 6.1.8. | Data Adjustments/Handling/Conventions | 31 |
| 6.2. | Special Handling for COVID-19 Disruptions | 32 |
| 7. | STUDY SUBJECTS AND DEMOGRAPHICS | 33 |
| 7.1. | Disposition of Subjects and Withdrawals | 33 |
| 7.2. | Protocol Deviations | 33 |
| 7.3. | Demographics and Other Baseline Characteristics | 33 |

| | | |
|--------|--|----|
| 7.4. | Exposure and Compliance | 34 |
| 8. | EFFICACY ANALYSIS | 35 |

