1. OVERVIEW

This statistical analysis plan (SAP) describes the planned analysis and reporting for Arcutis Biotherapeutics, Inc. protocol number ARQ-154-309 (A Phase 3, 8-Week, Parallel Group, Double Blind, Vehicle-Controlled Study of the Safety and Efficacy of ARQ-154 Foam 0.3% Administered QD in Subjects with Scalp and Body Psoriasis (ARRECTOR)), dated 29-Jul-2022, Amendment 3. Version 1 of the ARQ-154-309 SAP was based on protocol amendment 2 dated 12-May-2022 and was approved on 31-May-2022. Protocol Amendment 3, dated 29Jul2022, and SAP Version 2.0 (11-Aug-2022) were created to update the multiple testing strategy for secondary endpoints to reflect the change in the PSD secondary endpoints and to move SI-NRS change from baseline at Day 1 endpoint from Family 1 to Family 3 in the multiple testing strategy. The ARQ-154-309 database was locked on 09-Sep-2022 and unblinded on 12-Sep-2022. On 9-Sep-2022, FDA provided the following advice in preliminary feedback prior to a pre-NDA meeting for a similar program held on 14-Sep-2022.

For the primary estimand, you proposed a treatment policy strategy to handle all intercurrent events, including treatment discontinuation due to adverse event or lack of efficacy. For intercurrent events of treatment discontinuation due to adverse events or lack of efficacy, we recommend a composite strategy policy where subjects will be defined as non-responders, as we consider this to be the appropriate approach for handling such events. Your proposal to handle intercurrent events of treatment discontinuation using the treatment policy strategy can be used as part of a supportive estimand.

The purpose of this version of the SAP is to document the change to the primary estimand and related multiple imputation strategies. The revised estimand will be the focus of the Clinical Study Report and NDA. Key results based on the original estimand defined in SAP versions 1 and 2 will be provided as supplemental information for the primary and secondary endpoints covered by the multiple testing strategy.

Reference materials for this statistical plan include the protocol and the accompanying sample data collection documents. Operational aspects related to collection and timing of planned clinical assessments are not repeated in this SAP unless relevant to the planned analysis.

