6.1.4. Handling of Dropouts or Missing Data

6.1.4.1. Imputation of Missing Data

6.1.4.1.1. Imputation for the primary estimand

Any subject who prematurely withdraws from the study will have their last available data assigned to an analysis window as described in [Section 6.1.5](#). For subjects who discontinue due to lack of efficacy or adverse event, the last dose day will be assigned to an analysis window similarly as described in [Section 6.1.5](#). To comply with the definition of the primary estimand (Section 8.1.1), efficacy data assigned to a pre-specified analysis visit will be removed from the source data used for the multiple imputation process for visits on or after the assigned analysis visit of the last dose day for these subjects. Similarly, SI-NRS and WI-NRS weekly averages will be removed from the source data used for multiple imputation for weeks on or after the assigned analysis week of the last dose day for these subjects. This procedure will ensure that the data collected after intercurrent events are not used in the imputation process.

For the co-primary and secondary efficacy endpoints (i.e., S-IGA, B-IGA, weekly average SI-NRS, weekly average WI-NRS, total PSD score = 0, aggregated PSD score of itching, pain and scaling, PSD score of scaling item of 0, PSD score of the itching item of 0, PSD score of pain item=0, PASI, and PSSI), the analysis will impute missing values using a regression-based multiple imputation model. This is a three-step process.

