8.1. Primary Efficacy Analyses

The two co-primary efficacy endpoints of S-IGA Success and B-IGA Success at Week 8 will be analyzed using ITT population.

The S-IGA and B-IGA are ordinal scales with 5 severity grades which are reported only in integers. [Table 4](#) illustrates the description of each severity grade.

Table 4: S-IGA and B-IGA

| Score | Grade | Description |
|-------|--------------|---|
| 0 | Clear | Plaque thickening = no elevation or thickening over normal skin Scaling = no evidence of scaling Erythema = none (no residual red coloration but post-inflammatory hyperpigmentation may be present) |
| 1 | Almost Clear | Plaque thickening = none or possible thickening but difficult to ascertain if there is a slight elevation above normal skin level Scaling = none or residual surface drying and scaling Erythema = light pink coloration |
| 2 | Mild | Plaque thickening = slight but definite elevation Scaling = fine scales partially or mostly covering the lesions Erythema = light red coloration |
| 3 | Moderate | Plaque thickening = moderate elevation with rounded or sloped edges Scaling = most lesions at least partially covered Erythema = definite red coloration |
| 4 | Severe | Plaque thickening = marked or very marked elevation typically with hard or sharp edges Scaling = non-tenacious or thick tenacious scale, covering most or all of lesions Erythema = very bright red coloration; extreme red coloration; deep red coloration |

The co-primary estimands can be described by the following attributes:

Population: Subjects with Scalp and Body Psoriasis

Endpoints: S-IGA Success and B-IGA Success

Treatments: Roflumilast foam 0.3% vs. matching vehicle foam

Intercurrent events: Over the 8-week randomized treatment period, subjects may be exposed to possible known or unknown inter-current events that could impact the estimates of the estimand, such as treatment discontinuation due to a specific adverse effect or a lack of effect. A composite strategy will be implemented that handles subjects who discontinue due to lack of efficacy or adverse event as missing not at random, differently than all other subjects. Subjects who discontinue due to lack of efficacy or adverse event will be considered as non-responders (for MI and nonresponder imputation analyses) or missing (for observed case analyses) for all analysis visits (refer to Section 5.4) on or after the associated analysis visit of the subject's last dose day (refer to Section 6.1.5)

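### The SAP 6.1.7 rule that codes non-response is triggered by leaving the study, but the V3.0 composite estimand concerns stopping treatment

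*SAP*

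**What the plan says.** SAP Section 1 reproduces the regulatory advice behind V3.0: "For intercurrent events of treatment discontinuation due to adverse events or lack of efficacy, we recommend a composite strategy policy where subjects" are defined as non-responders. It says this version exists to document the resulting change to the primary estimand and imputation. It also gives the timing: "The ARQ-154-309 database was locked on 09-Sep-2022 and unblinded on 12-Sep-2022". The version history describes V3.0 as written after both.

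The sections that put the change into effect do not use one term:

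- **8.1, intercurrent event:** the example is "such as treatment discontinuation due to a specific adverse effect or a lack of effect".
- **8.1, rule:** "Subjects who discontinue due to lack of efficacy or adverse event will be considered as non-responders". What is discontinued is not stated.
- **6.1.4.1.1, primary imputation:** "For subjects who discontinue due to lack of efficacy or adverse event, the last dose day will be assigned to an analysis window". Again no object. Efficacy data from that visit onward are removed before imputation.
- **6.1.4.1.2, supplemental imputation:** "subjects who discontinue due to lack of efficacy or adverse event will be treated the same as those who did not discontinue" for those reasons.
- **6.1.4.2, tipping point:** relies on 6.1.7 and describes its effect as non-response from the point at which treatment stops.
- **6.1.7, derivation:** "subjects who discontinued early from study due to an AE or lack of efficacy will be considered as not having response". Categorical endpoints become non-response and continuous endpoints are set to baseline, from the analysis visit of the last dose. The V3.0 note in the version history has the same trigger: "for subjects who discontinued early from the study due to adverse event or lack of efficacy, a subject will be considered as non-responder".

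The documents treat the two events as different. Protocol 4.8.6 lists reasons for stopping IP. Protocol 4.8.7 lists reasons for leaving the study, and neither AE nor lack of efficacy is on that second list. SAP 9.1 counts treatment-emergent AEs leading to each separately.

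**The concern.** SAP 6.1.7 is the only derivation that sets a subject to non-response or to the baseline value. If its trigger is leaving the study, it misses one group: subjects who stop IP for an AE or lack of efficacy and remain for assessment. Those who also leave the study for these reasons are non-responders on every wording.

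For the missed group, the primary analysis would not apply the composite strategy that V3.0 was created to introduce and that Section 1 makes the focus of the study report and the NDA. Two programmers could also follow the text faithfully and obtain different primary data sets. As V3.0 postdates unblinding, the text should leave no choice about who enters the rule.

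**Working it through.** **Step 1. Trace one subject through the text.** Suppose a subject stops IP for an AE after Week 2, stays, and has a successful S-IGA at Week 8.

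| Reading of discontinue in 6.1.4.1.1 | Imputation source | 6.1.7 as written | Result |
|---|---|---|---|
| Leaves the study | Week 8 value kept | Not triggered | Observed success counts: treatment-policy handling, as for the supplemental estimand |
| Stops treatment | Values from the last-dose visit onward removed | Not triggered | Week 8 value re-imputed: neither composite nor treatment policy |
| Composite strategy as advised | Values removed | Would have to be triggered | Non-responder |

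Neither reading of 6.1.4.1.1, combined with 6.1.7 as written, gives the third row.

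**Step 2. What planned output would reveal.** Tables 14.3.1.7 (AEs leading to study drug discontinuation) and 14.3.1.8 (AEs leading to study discontinuation) are by arm, so comparing them indicates the AE part of the group. SAP 7.1 tabulates reasons for leaving the study only. No planned table gives IP stops for lack of efficacy, or how many of these subjects had a Week 8 assessment.

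**Step 3. Reproduce the plan's power.** Inputs from SAP 3.2 and 8.1.3: 280 active, 140 vehicle, two-sided alpha 0.025; S-IGA 46% vs 11%, B-IGA 32% vs 7%. SAP 3.2 names the arms in the reverse order; I take the higher rate as active. The unstratified normal approximation gives power above 0.99999 for S-IGA and 0.99999 for B-IGA, so the stated figure of more than 99% reproduces.

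**Step 4. How many reclassifications would overturn a co-primary?** Planned counts, rounded: S-IGA 129/280 vs 15/140; B-IGA 90/280 vs 10/140. Unstratified Mantel-Haenszel test, with a = active successes and m = all successes:

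χ² = (a − E)²/V, E = 280m/420, V = 280·140·m(420 − m)/(420²·419)

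- S-IGA: m = 144, E = 96, V = 21.08, χ² = 51.66, p = 6.6×10⁻¹³.
- S-IGA, 74 active successes removed: p = 0.0208. With 75 removed (54/280): E = 46, V = 12.84, χ² = 4.98, p = 0.0256.
- B-IGA: m = 100, E = 66.67, V = 16.97, χ² = 32.08, p = 1.5×10⁻⁸.
- B-IGA, 48 removed: p = 0.0213. With 49 removed (41/280): E = 34, V = 9.98, χ² = 4.91, p = 0.0267.

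No vehicle success is reclassified here, which is the least favourable case for the active arm.

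**Step 5. Effect of one subject on the estimates.** One reclassified success lowers an arm's rate by 1/280 = 0.36 points (active) or 1/140 = 0.71 points (vehicle).

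| | Planned OR | One active success reclassified | One vehicle success reclassified |
|---|---|---|---|
| S-IGA | (129×125)/(151×15) = 7.12 | (128×125)/(152×15) = 7.02 (−1.4%) | (129×126)/(151×14) = 7.69 (+8.0%) |
| B-IGA | (90×130)/(190×10) = 6.16 | (89×130)/(191×10) = 6.06 (−1.6%) | (90×131)/(190×9) = 6.89 (+12.0%) |

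**Step 6. A range, as an assumption.** If 0 to 5% of the active arm (0 to 14 of 280) stop IP for these reasons and stay, and their observed success lies between zero and the arm's rate, the 6.1.7 wording with observed results kept raises the active rate over the composite by 0 to 0.05×46 = 2.3 points (S-IGA) and 0 to 0.05×32 = 1.6 points (B-IGA).

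**The case against.** The best reply is that the intent is clear. The cut-off is everywhere the last dose day, not study exit, and 6.1.4.2 cites 6.1.7 as the rule that makes subjects non-responders once treatment stops. On this view one word is loose and the estimand is intact. I agree that this is probably what was meant. But the last dose day fixes when the rule starts, not who enters it. The study reading also has support: 6.1.4.1.1 opens with subjects who withdraw from the study, and the version note uses the same trigger as 6.1.7.

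The group may also be empty. Protocol 5.9 speaks of AEs warranting discontinuation from the study, and one item in 4.8.6 refers to risk if the subject continues in the study. Lack of efficacy appears in neither removal list. The follow-up sentence in Protocol 4.8.5 concerns unblinding, and following a recurrent application site reaction to resolution is AE follow-up, not retention for Week 8 efficacy. All of this stands. It limits the size of the problem; it does not make the wording consistent.

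Three stronger readings are tempting, and the documents do not support them:

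- **That these subjects necessarily keep their observed result in both the primary and supplemental tables (14.2.1.1 and 14.2.1.1.s).** That holds only if 6.1.4.1.1 means leaving the study. Otherwise their data are re-imputed in the primary analysis and the tables could differ.
- **That nothing planned shows the size of the group.** Tables 14.3.1.7 and 14.3.1.8 indicate its AE part.
- **That the wording was chosen after unblinding to favour the active arm.** Section 1 dates the advice to 9 September 2022, before unblinding, and the direction of any effect depends on an unknown split between arms.

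**Conclusion.** The inconsistency is real and should be fixed. As written, 6.1.7 does not code non-response for subjects who stop IP because of an AE or lack of efficacy and remain in the study, although Section 1, the example in 8.1 and 6.1.4.2 all point to treatment discontinuation as the event.

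Its size is unknown and may be zero. The co-primary conclusions are not at risk at the planned rates. Reported rates and odds ratios can move by the per-subject amounts above, in either direction. The secondary endpoints inherit the same rule, and Family 2 is tested sequentially at 0.005, but the documents give no expected rates from which to put a figure on that effect.

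The calculations assume planned rather than observed counts, no stratification or imputation, and the higher SAP 3.2 rate as active.

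**What to change.** - **One trigger** in 6.1.4.1.1, 6.1.4.1.2, 6.1.4.2, 6.1.7 and 8.1: *permanently discontinued IP due to AE or lack of efficacy, whether or not the subject remained in the study*. Name its eCRF source, including how lack of efficacy is identified as the reason for stopping IP.
- **Scope:** apply the rule to observed and missing values alike, from the analysis visit of the last dose onward.
- **Table 14.1.1:** add, by arm, the reasons for IP discontinuation and the number who stopped IP for AE or lack of efficacy but had a Week 8 assessment.
- **Both triggers:** because any change now follows unblinding, report the co-primary and multiplicity-controlled secondary results under both the IP-discontinuation and the study-discontinuation trigger.

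The cost is wording in five sections, extra rows in one table and a rerun of the derivations and affected analyses. Reported success rates may fall slightly. If the new disposition rows show that nobody stopped IP for these reasons and stayed, the two sets of results will coincide and the point closes.
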